##### **Use of stored human biospecimens for research (section 3.2.2):**

[This study will not use previously stored biospecimens for its purposes. However, consent will be sort from participants to store a small sample of blood post completion of the study. Specific consent will be sort for this in the Patient Information and Consent Sheet. The purpose of this relates to the embryonic understanding of the neuro-endocrine, inflammatory and immune involvement in POTS and LCS. It is foreseeable that emerging understanding of these conditions may elucidate contributing pathophysiology. Stored samples from these cohorts could allow for further studies to be undertaken without the added burden of additional blood draw. Stored samples would not be utilised for such purposes without appropriate ethics approval.]

##### **Use of only stored biospecimens with no more than low risk (section 3.2.3)**

[Not relevant to this study. ]

#### Element 2: Recruitment

##### **Prospective collection of human biospecimens for research (section 3.2.4):**

**Burden justified by potential benefits:** [Type response here]

- (a) Burden justified by potential benefits:** [The burdens of the blood collection on the donor(s) are justified by the potential benefits of this proposed research. POTS and LCS have a significant patient burden in terms of reduced quality of life and high community and health care burden. This study has the potential to elucidate biomarkers that inform understanding of disease aetiology, diagnosis and treatment which may in turn lead to mitigation of these burdens.]
- (b) Suitable qualification and experience of those involved in collection:** [Blood collection will be undertaken via a qualified and registered pathology collection service as well as by clinically trained and qualified researchers. These researchers include medical doctors and registered nurses who are experienced in the practices of safe blood collection and will adhere to best practice guidelines for phlebotomy. All blood collection will be undertaken in an appropriate clinical setting.]

(c) **Arrangements for intended processing, storage, distribution and/or use, and disposal of biospecimens:** [Blood specimens will be deidentified, spun in a centrifuge and frozen and stored in locked bio-secure freezers at the South Australian Health and Medical Research Institute to facilitate analysis.

Routine blood samples will be processed in accordance with current guidelines as detailed by the associated, accredited pathology group. Blood samples will be deidentified and coded before being sent to the pathology provider. Not participant details will be shared with third party providers.

Blood sample analysis undertaken by the researchers are detailed below. The principal investigator will be responsible for the permanent and safe disposal of samples as per University of Adelaide policies that govern safe handling of bio-specimens.

- ELISA kits to detect autoantibodies against the  $\alpha 1$  adrenergic b-1 adrenergic, M1 receptors and M4 muscarinic cholinergic receptor antibodies will be purchased from CellTrend GmbH (Luckenwalde, Germany). Samples will be processed as per the manufacturer's instruction
- Inflammatory biomarkers will be processed using ProcartaPlex™ Multiplex Immunoassay as per manufacturer's instructions.
- Copeptin: Morning blood test with a 8 hr food fast (drink to thirst). Plasma will be collected in EDTA tubes, centrifuged and kept in -80 degrees freezer before batch analysis using the Thermo Scientific B·R·A·H·M·S Copeptin proAVP KRYPTOR assay using B·R·A·H·M·S KRYPTOR compact PLUS, Hennigsdorf, Germany). All data will be deidentified and stored as per above procedures

#### **Human biospecimens obtained After death for research (section 3.2.5)**

[Not applicable to this study]

#### **Use of human biospecimens collected for clinical purposes (section 3.2.6)**

~~[Human biospecimens that have been obtained for clinical purposes and have been retained by an accredited clinical pathology service may be utilised in this study. The identity of the donor is not necessary for this activity and samples will be de-identified for this purpose. Not applicable to this study]~~

#### **Importation and exportation of human biospecimens for research (section 3.2.7 – 3.2.9)**

[There is no intention to export or import human biospecimens for this study.]

#### **Transitioning provisions for existing biospecimens (section 3.2.10)**

[Not applicable as the biospecimens for this study will not be obtained before December 2013]

#### **Element 3: Consent**

##### **Prospective collection of human biospecimens for research (sections 3.2.11, 3.2.12):**

**Consent forms for donors will be obtained and recorded (3.2.11)**

**Information given to participants before obtaining consent is (section 3.2.12):**

- (a) research for which the biospecimens are to be used;
- (b) how specimens will be stored, used and disposed of including processes to respect their personal or cultural sensitivities;
- (c) extent to which the biospecimens will be reasonably identifiable and how privacy and confidentiality will be respected;
- (d) whether the research is likely to provide information that may be important to their health or to the health of their relatives or their community;
- (e) if (d) applies, whether or not they will have the choice to receive this information and how this will be managed;
- (f) if (d) applies, whether or not they will have the choice for it to be provided to their relatives or to their community and how this will be managed;
- (g) whether the biospecimens and associated data may be distributed to other researchers, including those outside Australia;
- (h) right to withdraw consent for continued use of their biospecimens or associated data and any limitations that may be relevant;
- (i) financial or personal interests that those engaged in the collection, processing storage and distribution and use of their biospecimens may have; and
- (j) any potential for commercial application of any outcomes of the research.

(a): The Patient Information Sheet contains information that informs the participants of why the biospecimens are important to the research. Unspecified consent and future use of blood samples are described and requested in the patient consent form.

(b): Plasma will be collected in EDTA tubes, centrifuged and kept in -80 degrees freezer at the locked University of Adelaide Laboratory, Level 6 laboratory, SAHMRI, before batch analysis. The principal investigator will oversee appropriate destruction of samples in accordance with University and Laboratory protocols that detail the safe and respectful disposal of human biospecimens. The date, time and method of destruction of the samples will be recorded in the lab archives and stored for a minimum of 10 years on the University encrypted, electronic platform. The specimens will only be used in the manner to which consent was granted for their use.

(c): Participant medical information will be stored electronically on an encrypted server within the Centre for Heart Rhythm Disorders. Identifiable information such as names, birthdates, contact details, and medical record numbers will not be stored with biospecimens but rather will be replaced with a linkage code. Access to participant medical information contained within the database will be restricted to CHRD investigators named on this protocol.

Information linking the linkage codes to the participants' identifiable information will be stored in a secure location separate from the biospecimen. Access to the information linking the linkage codes with information that may identify participants will be granted only to CHRD investigators named on this protocol on a need-to-know basis as approved by the Principal Investigator of POTS-LCS. Access to the information linking the linkage codes with participant identifiers shall be documented.

Blood samples will be stored by the principal investigator in the University of Adelaide CHRD locked laboratory at the South Australian Health and Medical Research Building, and recorded in the University's metadata store. All access to said samples will be approved by the Principal Investigator and logged in the study logbooks.

(d): Use of biospecimens in this study are predominantly exploratory. Results of testing of inflammatory/immune markers will not be able to be deemed of clinical significance due to lack of current understanding of these conditions. Therefore, the outcomes of these biospecimen analysis would not result in information about a participant's future health ~~or risk of having children with a genetic disorder,~~ or information that may be relevant to the health of family members who are not part of the trial. However, routine blood and urine tests may indicate 'out of range' results that could be of significance to current health and therefore will be shared (with consent) to the participants nominated general practitioner.

(e): ~~Not applicable~~ Participants will have the choice to nominate and consent for results to be shared with their treating general practitioner

(f): ~~Not applicable~~ These results will not be relevant to family or community as they pertain to routine blood and urine results and not to gene or other markers that may affect communities or families.

(g): Associated data from the analysis of biospecimens will be uploaded to 'figshare' for international collaborative research use. No identifiable information will be shared. Remaining biospecimens will be stored for future use from the same research group. The patient consent form asks for consent for the same and other researchers to use remaining samples for future research. There is no intention or request of participants for use of their samples for exportation.

(h): Traceability of the blood samples and data will remain possible in order to enable participant withdrawal. On application of withdrawal participant's biospecimens will be destroyed as per University of Adelaide protocols pertaining to the safe handling and destruction of human tissue. Where samples have already been included in research analysis it will not be possible to withdraw this data. This is detailed in the PICF. However remaining specimens will be destroyed in a manner that allows for sensitivity to cultural and religious practices as requested by individuals and their respective communities.

(i): The researchers have no other relevant financial interests pertaining to the collection, storage and use of the biospecimens.

(j): There are no foreseeable commercial applications of any of the outcomes of this research involving collection of biospecimens.

#### **Use of stored human biospecimens for research (section 3.12.13 – 3.12.14)**

[The blood specimens in this study will only be used in the manner detailed on the patient consent form. Samples will be de-identified and replaced with a traceable code. This will allow for re-contact of the donor for future consent of use of their biospecimen in research. ]

#### **Element 5: Communication of research findings or results to participants (section 3.2.15):**

**Where proposed research involving use of human biospecimens may be important for the health of the donors, their relatives or their community, researchers should prepare an ethically defensible plan to describe management of any proposed disclosure or non-disclosure of that information including the elements in (a) – (i).**

[As per element d) above. The results of biospecimen analysis in this study do not pertain to genetic or other information that would be deemed relevant and important information for the health of the donor and/or their family and community. As such there is no plan for communication of the analysis

results to the individual, family or community. However results from routine blood and urine samples undertaken in this study may be deemed clinically significant for current or future comparison and therefore copies of the results of these will be forwarded to participants nominated general practitioner. Consent for sharing of this information will be included in the consent form. ]

# 36- Item Short Form Survey Instrument (SF-36)

## RAND 36-Item Health Survey 1.0 Questionnaire Items

Choose one option for each questionnaire item.

1. In general, would you say your health is:

- 1 - Excellent
  - 2 - Very good
  - 3 - Good
  - 4 - Fair
  - 5 - Poor
- 

2. **Compared to one year ago**, how would you rate your health in general **now**?

- 1 - Much better now than one year ago
  - 2 - Somewhat better now than one year ago
  - 3 - About the same
  - 4 - Somewhat worse now than one year ago
  - 5 - Much worse now than one year ago
-

The following items are about activities you might do during a typical day. Does **your health now limit you** in these activities? If so, how much?

	Yes, limited a lot	Yes, limited a little	No, not limited at all
3. Vigorous activities , such as running, lifting heavy objects, participating in strenuous sports	 1	 2	 3
4. Moderate activities , such as moving a table, pushing a vacuum cleaner, bowling, or playing golf	 1	 2	 3
5. Lifting or carrying groceries	 1	 2	 3
6. Climbing several flights of stairs	 1	 2	 3
7. Climbing one flight of stairs	 1	 2	 3
8. Bending, kneeling, or stooping	 1	 2	 3
9. Walking more than a mile	 1	 2	 3
10. Walking several blocks	 1	 2	 3
11. Walking one block	 1	 2	 3
12. Bathing or dressing yourself	 1	 2	 3

---

During the **past 4 weeks**, have you had any of the following problems with your work or other regular daily activities **as a result of your physical health**?

- |                                                                                                       | Yes                        | No                         |
|-------------------------------------------------------------------------------------------------------|----------------------------|----------------------------|
| 13. Cut down the amount of time you spent on work or other activities                          | 
1 | 
2 |
| 14. Accomplished less than you would like                                                      | 
1 | 
2 |
| 15. Were limited in the kind of work or other activities                                       | 
1 | 
2 |
| 16. Had difficulty performing the work or other activities (for example, it took extra effort) | 
1 | 
2 |
- 

During the **past 4 weeks**, have you had any of the following problems with your work or other regular daily activities **as a result of any emotional problems** (such as feeling depressed or anxious)?

- |                                                                              | Yes                     | No                      |
|------------------------------------------------------------------------------|-------------------------|-------------------------|
| 17. Cut down the amount of time you spent on work or other activities |  1 |  2 |
| 18. Accomplished less than you would like                             |  1 |  2 |
| 19. Didn't do work or other activities as carefully as usual          |  1 |  2 |
- 

20. During the **past 4 weeks**, to what extent has your physical health or emotional problems interfered with your normal social activities with family, friends, neighbors, or groups?

- 1 - Not at all
  - 2 - Slightly
  - 3 - Moderately
  - 4 - Quite a bit
  - 5 - Extremely
-

21. How much **bodily** pain have you had during the **past 4 weeks**?

- 1 - None
  - 2 - Very mild
  - 3 - Mild
  - 4 - Moderate
  - 5 - Severe
  - 6 - Very severe
- 

22. During the **past 4 weeks**, how much did **pain** interfere with your normal work (including both work outside the home and housework)?

- 1 - Not at all
  - 2 - A little bit
  - 3 - Moderately
  - 4 - Quite a bit
  - 5 - Extremely
-

These questions are about how you feel and how things have been with you **during the past 4 weeks**. For each question, please give the one answer that comes closest to the way you have been feeling.

How much of the time during the **past 4 weeks**...

- |                                                                         | All of
the
time   | Most
of the
time  | A good
bit of the
time | Some
of the
time  | A little
of the
time | None
of the
time  |
|-------------------------------------------------------------------------|-------------------------|-------------------------|------------------------------|-------------------------|----------------------------|-------------------------|
| 23. Did you feel full of pep?                                           |  1 |  2 |  3      |  4 |  5    |  6 |
| 24. Have you been a very nervous person?                                |  1 |  2 |  3      |  4 |  5    |  6 |
| 25. Have you felt so down in the dumps that nothing could cheer you up? |  1 |  2 |  3      |  4 |  5    |  6 |
| 26. Have you felt calm and peaceful?                                    |  1 |  2 |  3      |  4 |  5    |  6 |
| 27. Did you have a lot of energy?                                       |  1 |  2 |  3      |  4 |  5    |  6 |
| 28. Have you felt downhearted and blue?                                 |  1 |  2 |  3      |  4 |  5    |  6 |
| 29. Did you feel worn out?                                              |  1 |  2 |  3      |  4 |  5    |  6 |
| 30. Have you been a happy person?                                       |  1 |  2 |  3      |  4 |  5    |  6 |
| 31. Did you feel tired?                                                 |  1 |  2 |  3      |  4 |  5    |  6 |

---

32. During the **past 4 weeks**, how much of the time has **your physical health or emotional problems** interfered with your social activities (like visiting with friends, relatives, etc.)?

- 1 - All of the time
  - 2 - Most of the time
  - 3 - Some of the time
  - 4 - A little of the time
  - 5 - None of the time
-

How TRUE or FALSE is **each** of the following statements for you.

	Definitely true	Mostly true	Don't know	Mostly false	Definitely false
33. I seem to get sick a little easier than other people	 1	 2	 3	 4	 5
34. I am as healthy as anybody I know	 1	 2	 3	 4	 5
35. I expect my health to get worse	 1	 2	 3	 4	 5
36. My health is excellent	 1	 2	 3	 4	 5

---

## ABOUT

The RAND Corporation is a research organization that develops solutions to public policy challenges to help make communities throughout the world safer and more secure, healthier and more prosperous. RAND is nonprofit, nonpartisan, and committed to the public interest.

[name]  
[name]

---

RAND® is a registered trademark. Copyright © 1994-2016 RAND Corporation.

## **Health Questionnaire**

### **English version for Australia**

Under each heading, please tick the ONE box that best describes your health TODAY.

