## SECTION 2: NATURE OF THE PROJECT

### 2.1 Aims of the project:

Discuss in standard English the main research aims/hypotheses to be investigated.

The primary objective of this study is to:

[1] Assess the prevalence of POTS in those with LCS, using a standardised and detailed autonomic testing protocol

The secondary objectives of this study include:

[2] Characterising the neuroendocrine/inflammatory/immune biomarker profile of those with LCS(+)/POTS/LCS(-)/POTS and POTS and compare to matched, healthy controls

[3] Determining the impact of LCS with and without POTS and POTS on quality of life & symptom scores, cognitive function and psychological well-being and compare to matched, healthy controls

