### Study testing day:

The following testing protocol will take approximately 60-90 minutes to complete. A schematic representation of the protocol can be seen (Figure 1: above)

Non-invasive measurements of continuous arterial pressure and heart rate will be obtained using finger photoplethysmography (non-invasive blood pressure testing; NIBP) for 5 minutes before testing (rest) and then during each reflex test. This involves application of a small cuff to either of the 2nd to 5th digits of

one hand. The cuff is inflated to allow measurement of finger arterial blood pressure. This technique is well validated in a variety of clinical and experimental conditions and is similar to our prior protocol. Description of each test can be found in section 3.16

Testing variables	Cohort 1	Cohort 2	Cohort 3
Demographic Survey	X	X	X
Medical health history	X	X	X
Medications use	X	X	X
Physical examination	X	X	X
Health Related QoL			
- SF-36 [36-Item Short Form Survey]	X	X	X
- EQ-5D [5 level EQ score]	X	X	X
- COMPASS-31 [composite autonomic symptom scale]	X	X	X
- FSS [fatigue severity score]	X	X	X
- 5 Point hypermobility screen	X	X	X
- OHQ [orthostatic hypotension questionnaire]	X	X	X
Autonomic testing			
- Standing test, deep breathing, Valsava manoeuvre	X	X	X
- Sudomotor function (SUDOSCAN)	X	X	X
- 24-hour Holter monitoring	X	X	X
- Echocardiogram with Passive Leg Raise	X	X	X
Blood tests:			
- Complete Blood Panel and Electrolytes, CRP, ESR,	X	X	X
# TNF- $\alpha$ , IL-6, IL-1 $\beta$ , IL-10, IL-21, INF $\gamma$ , INF $\alpha/\beta$ , CD30,	X	X	X
# $\alpha$ 1 adrenergic, Beta-1 adrenergic, M1 and M4 muscarinic	X	X	X
cholinergic receptor Ab;			
# Aldosterone, Potassium, Renin activity, copeptin level;	X	X	X
# Plasma Histamine, heparin, chromogranin A	X	X	X
24 hr Urinary volume and osmolarity	X	X	X
Cognitive and psychological testing			
- CANTAB (Cambridge neuropsychological test automated battery)	X	X	X
- HADS (hospital anxiety and depression scale)	X	X	X

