**Before study testing day:**

In addition, all study participants will be sent a link to a health questionnaire and QoL surveys as listed below. These can be done at leisure and without time restriction to reduce the effects of inconvenience and survey fatigue.

1. Holter Monitor: All patients will undergo 24 hour ambulatory ECG, at home (adhesive electrodes placed on the skin and attached to a recording device). This measure will be used to determine heart rate variability; which is a measure of baseline autonomic tone. It will also help to exclude other alternative cardiac arrhythmias.
2. Echocardiogram requires the subject to undertake an ultrasound of the heart previous to the day of testing at the subject's convenience. This test is important for determining other secondary causes of symptoms due to structural cardiac changes. It requires a non-invasive ultra-sound of the heart and generally takes 15 minutes to complete. To determine associations of neuroendocrine function with changes to orthostatic filling volumes and cardiac measurements. Echocardiogram will be undertaken in the semi-fowler position and then in passive leg raise (45 degree) position after 90 seconds.
3. Demographic survey and Medical Health History including alcohol consumption, tobacco use. Past medical history, medications and allergies will be completed by the two symptomatic cohorts.

Controls will complete a health history and demographic survey to confirm absence of exclusion medical conditions and medications when attending for assessment.

4. Rand SF-36: 36 item short form survey which is commonly utilised to measure self-reported quality of life measures in adult patients.
5. EQ-5D/5L: Is a short survey utilised and validated to describe and value health across 5 domains.
6. COMPASS-31: 31 question composite autonomic scale which is utilised widely for use in autonomic research and practice. It addresses the domains of: orthostatic intolerance, vasomotor, secretomotor, gastrointestinal, bladder and pupillomotor function.
7. Fatigue Severity Score: A 9 item questionnaire that reports how fatigue interferes with certain activities and rates the severity of fatigue.
8. 5 Point hypermobility screen: Five questions related to hypermobility. A score  $>2/5$  suggests hypermobility (sens 85%, spec 90%)

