### 5.5 How will participant data, samples and information be analysed and who will undertake this analysis?

[name] will perform the primary analysis of the physiological data with supervision from the listed researchers. Continuous variables will be reported as mean and standard deviation, or median and interquartile range, as appropriate to distribution. Count variables will be reported as numbers and percentages. Categorical variables will be evaluated using a chi-square or Fisher exact test as appropriate. All statistical tests will be two-sided, and a p value of <0.05 will be considered significant. All analyses will be undertaken using Stata 13.0 (Stata Corporation).

Some routine blood samples and urine will be analysed at a third party, accredited pathology service. The samples will be de-identified and coded in an unidentifiable way. No patient details will be sent to the pathology service. Blood sample analysis undertaken by the researchers detailed below at University of Adelaide Laboratories, SAHMRI. These samples will be analysed according to the following protocols.

- ELISA kits to detect autoantibodies against the  $\alpha 1$  adrenergic b-1 adrenergic, M1 receptors and M4 muscarinic cholinergic receptor antibodies will be purchased from CellTrend GmbH (Luckenwalde, Germany). Samples will be processed as per the manufacturer's instructions.
- Inflammatory biomarkers will be processed using ProcartaPlex™ Multiplex Immunoassay as per manufacturer's instructions
- Copeptin: Morning blood test with a 8 hr food fast (drink to thirst). Plasma will be collected in EDTA tubes, centrifuged and kept in -80 degrees freezer before batch analysis using the Thermo Scientific B·R·A·H·M·S Copeptin proAVP KRYPTOR assay using B·R·A·H·M·S KRYPTOR compact PLUS, Hennigsdorf, Germany). All data will be deidentified and stored as per above procedures

**5.6 What feedback of findings will be offered to participants e.g. access to transcripts of interviews, drafts or final reports? When will this occur? If no feedback will be offered, outline why.**

It is good practice to provide participants with the opportunity to review any transcripts, particularly if they will be named or there is the potential for them to be identifiable in the research findings.

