**MOBILITY**

- I have no problems with walking around
- I have slight problems with walking around
- I have moderate problems with walking around
- I have severe problems with walking around
- I am unable to walk around

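### Section 5.5 sends every categorical variable to chi-square or Fisher exact; if the five-level EQ-5D-5L dimensions are compared under that rule, their order is discarded and power falls

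*Protocol*

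**What the plan says.** Section 5.5 of the protocol has three relevant statements.

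- Continuous variables get a descriptive summary: "Continuous variables will be reported as mean and standard deviation, or median and interquartile range, as appropriate to distribution".
- Categorical variables get a test: "Categorical variables will be evaluated using a chi-square or Fisher exact test as appropriate".
- The significance level is set for all tests: "All statistical tests will be two-sided, and a p value of <0.05 will be considered significant".

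No other between-group test is named there. The qualifier in the second statement chooses between chi-square and Fisher. It does not open the door to a third method.

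The EQ-5D is listed for all three cohorts in the Section 2.5 testing table as "EQ-5D [5 level EQ score", and Section 3.16 describes it thus: "EQ-5D/5L: Is a short survey utilised and validated to describe and value health across 5 domains". It serves secondary objective 3 in Section 2.1: "Determining the impact of LCS with and without POTS and POTS on quality of life & symptom scores". The attached form carries the instruction "Under each heading, please tick the ONE box that best describes your health TODAY". Each dimension runs through five ordered levels; mobility starts at "I have no problems with walking around" and ends at being unable to walk. The form closes with a 0-100 rating of health today.

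**The concern.** A single tick among five graded answers is an ordered categorical variable. Read literally, Section 5.5 would cross-tabulate level by group and apply chi-square or Fisher. Both give the same result however the five columns are permuted, so the information that level 4 is worse than level 3 is not used. The two-group chi-square spreads its sensitivity over 4 degrees of freedom, while a shift along the scale needs only 1.

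Objective 3 is about impact, and some contrasts that serve it are small: 34 with POTS, 34 controls, and about 15 LCS participants with POTS at the protocol's own 10% prevalence (0.10 × 150). The same answers analysed with a method that uses order would give a better chance of detecting a consistent worsening. The test also supplies no effect size.

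**Working it through.** **The plan's own figures.** Section 3.3 has no power or sample-size statement for any quality-of-life outcome, so there is none to reproduce on this point. Its two calculations concern POTS prevalence (1.96² × 0.1 × 0.9 / 0.05² = 138.3, so 139, as stated) and orthostatic heart rate (81.5% by recalculation at 15 per group, against a stated 80%). Neither bears on the EQ-5D.

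**Inputs from the protocol.** Five ordered levels per dimension (EQ-5D form); two-sided alpha 0.05 (Section 5.5); groups of 150, 34 and 34 (Section 2.5).

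**Inputs assumed.** The protocol gives no distribution of answers and no effect size for the EQ-5D. The simulations assume a proportional-odds shift, with the odds ratios and base distributions shown.

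**Step 1: degrees of freedom.** With g groups and k levels, chi-square has (g−1)(k−1) degrees of freedom; a test for an ordered shift has g−1. For two groups and five levels this is 4 against 1; for four groups, 12 against 3.

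**Step 2: noncentrality needed for 80% power, two groups.** It is 7.85 on 1 df and 11.94 on 4 df. Since noncentrality grows in proportion to sample size:

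- effective sample = 7.85 / 11.94 = 0.66;
- sample needed by chi-square = 11.94 / 7.85 = 1.52 times as large;
- power of the 4-df test at noncentrality 7.85 = 59.5%.

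**Step 3: how far the ratio moves.**

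| Groups | 70% power | 80% power | 90% power |
|---|---|---|---|
| 2 | 0.64 | 0.66 | 0.68 |
| 3 | 0.62 | 0.64 | 0.66 |
| 4 | 0.61 | 0.63 | 0.65 |

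Collapsing levels softens the loss. For two groups at 80% power the ratio is 0.72 with four levels and 0.81 with three.

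**Step 4: simulation at planned sizes.** Power of Pearson chi-square against the tie-corrected Wilcoxon test, odds ratio 3.5, 3000 runs per setting. Base distributions: even (0.20 in each level), skewed (0.50, 0.25, 0.15, 0.07, 0.03) and ceiling (0.80, 0.12, 0.05, 0.02, 0.01).

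| Base distribution | 34 v 34 | 150 v 34 |
|---|---|---|
| Even | 59% v 81% | 88% v 96% |
| Skewed | 56% v 80% | 82% v 95% |
| Ceiling | 40% v 67% | 54% v 86% |

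For 34 v 34, chi-square needed about 51 per group to reach what the rank test reaches at 34 (34/51 = 0.67, in line with Step 2). With 15 v 135 (the LCS split at 10% prevalence) and an assumed odds ratio of 3, separate runs gave chi-square 36-49% against 60% for the rank test. With no true difference, the rank test rejected in about 4% to 6% of runs. Chi-square was near 5% in most settings and as low as 2% with the ceiling distribution at 34 v 34.

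**Step 5: Fisher.** Sparse tables would push the analyst to Fisher. At the planned sizes Fisher had 36-59% power against 58-76% for the rank test, a loss similar to that of chi-square.

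**The case against.** The strongest objection is that the protocol never says the EQ-5D dimensions will be tested by chi-square or Fisher. Its own wording leans at least partly towards a score: the testing table calls it a score, Section 3.16 speaks of valuing health, objective 3 refers to scores, and the form includes a 0-100 scale. Section 5.5 is also plainly not a complete list of tests, because it names none for continuous variables. Scoring rules and item-level tests are commonly left to a statistical analysis plan. **This stands as a limit on scope.** A reader might infer that the EQ-5D comparison will in fact run on two thirds of its sample; the documents do not support that. The loss is conditional on a dimension-level comparison.

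It does not remove the point. The rule for categorical variables is a stated choice with no carve-out for ordered ones, rather than a gap left for later.

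A second objection is that the questionnaire instruction contains no error. That is right: it shows the answer format, and the text to change is Section 5.5.

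Third, a reader might conclude that real worsening will often be missed. That too goes further than the documents allow, since it rests on assumed odds ratios and distributions. At 150 v 34 with odds ratio 3.5, chi-square still has 82-88% power under the even and skewed distributions.

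Fourth, the aims state no direction and the tests are two-sided. A two-sided rank test needs no directional hypothesis, so this does not weaken the point. It is true that the direction of a difference could be read from the reported percentages; what the test lacks is an effect size.

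**Conclusion.** The point holds in conditional form. Section 5.5 prescribes an order-blind test for all categorical variables, and the EQ-5D-5L dimensions are ordered. If they are compared between groups under that rule, a monotone shift between two groups is tested with about 60% power where an ordered test would have 80%. The effective sample is about 0.61 to 0.68 across two to four groups and 70% to 90% power.

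This assumes dimension-level analysis, uncollapsed levels and a monotone shift. The simulated powers additionally assume odds ratios and base distributions that the protocol does not give. The loss is zero for an index value or the 0-100 scale, either of which the protocol permits. Quality of life is a secondary objective without a power claim, so no stated sample size and no primary result is affected. The change is worth making because the better method costs almost nothing.

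**What to change.** In Section 5.5, restrict chi-square and Fisher exact to nominal and yes/no variables, and add a sentence such as: *Ordered categories, including any dimension-level comparison of the EQ-5D-5L, will be compared by the Wilcoxon rank-sum test (two groups) or the Kruskal-Wallis test (several groups), with a common odds ratio and 95% confidence interval from a proportional-odds model.* It would help to state there which EQ-5D summary is to be compared: dimension levels, index value or the 0-100 scale.

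The cost is a sentence or two. No new data, visits or participants are needed, and the software named in Section 5.5 can run these methods. There is a small downside: rank tests are less sensitive to a difference that is not monotone across levels, and the common odds ratio relies on proportional odds.
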